I have read this protocol and agree that it contains all the necessary details for performing the study in accordance with the Declaration of Helsinki and the International Conference on Harmonization (ICH) for Good Clinical Practice (GCP).

I will provide copies of the protocol and of the clinical and preclinical information on the investigational product, which was furnished to me by the Sponsor, to all members of the study team responsible to me who participate in the study. I will discuss this material with them to assure that they are fully informed regarding the study drug and the conduct of the study.

I will perform the study according to specifications outlined in the protocol and agree to implement protocol requirements only after the protocol and patient information/Informed Consent form have been approved by the Institutional Review Board/Ethics Committee (IRB/EC). I will submit any protocol modifications (amendments) and/or any Informed Consent form modifications to the IRB/EC, and approval will be obtained before any modifications are implemented.

I understand that the information presented in this study protocol is confidential, and I hereby assure that no information based on the conduct of the study will be released without prior consent from the Sponsor, Revance Therapeutics, Inc. unless this requirement is superseded by a regulatory authority (e.g., FDA).

Investigator Name (PLEASE PRINT)

Signature:	Date	
0		

SYNOPSIS

TITLE OF STUDY: A Phase 2, Randomized, Double-Blind, Placebo-Controlled, Parallel Group, Dose-Ranging, Multi-Center Trial to Evaluate the Efficacy and Safety of DaxibotulinumtoxinA for Injection for the Treatment of Upper Limb Spasticity in Adults After Stroke or Traumatic Brain Injury (JUNIPER)

NAME OF SPONSOR(S): Revance Therapeutics, Inc

NAME OF INVESTIGATIONAL PRODUCT: DaxibotulinumtoxinA for Injection

STUDY CENTERS: Up to 35 study centers across the United States

PLANNED NUMBER OF SUBJECTS: Approximately 128 subjects

DURATION OF STUDY: Up to 39 weeks, including 3 weeks for screening

Clinical Phase: 2

OBJECTIVES

Primary Objective

 To compare the safety and efficacy of a single treatment of DaxibotulinumtoxinA for Injection (DAXI for injection) at three dose levels (250 U, 375 U, 500 U) versus placebo in reducing muscle tone of adult subjects with upper limb spasticity after stroke or traumatic brain injury

DaxibotulinumtoxinA for Injection for Adult Upper Limb Spasticity
Protocol 1820203 Amendment 3

Version 6 29 June 2020

STUDY DESIGN
This randomized, double-blind, placebo-controlled trial will evaluate the dose-related efficacy
and safety of 3 doses of DAXI for injection for the treatment of upper limb spasticity (ULS) in
adult subjects.
Approximately 128 adult subjects with upper limb spasticity after stroke or traumatic brain
injury will be recruited from up to 35 study centers across the United States (US). The
Screening period will be up to 21 days
Screening period will be up to 21 days.

DaxibotulinumtoxinA for Injection for Adult Upper Limb Spasticity Protocol 1820203 Amendment 3	Version (29 June 202(

DaxibotulinumtoxinA for Injection for Adult Upper Limb Spasticity	Version 6
Protocol 1820203 Amendment 3	29 June 2020
d.	
SUBJECT REPLACEMENT STRATEGY: Subjects who discontinue from the study will r	not be
replaced.	

ELIGIBILITY CRITERIA

Inclusion Criteria

- 1. Adults, 18 to 75 years of age, inclusive.
- 2. Written informed consent including authorization to release health information.
- 3. Focal upper limb spasticity (ULS) after a stroke (as defined by WHO criteria) or traumatic brain injury (TBI), last stroke or TBI > 24 weeks prior to Screening.
- ULS with the primary aggregate posture (AP): flexed elbow + flexed wrist + clenched fist (flexed fingers) and ≥ 1 other clinical pattern(s): adducted and internally rotated shoulder, pronated forearm, and/or thumb-in-palm deformity.
- 5. Moderate to severe ULS with a MAS score ≥ 2 at the elbow, wrist, and finger flexors; with the exception that the MAS score is ≥ 3 at the suprahypertonic muscle group (SMG) for subjects with previous injections of BoNTA in the paretic limb.
- Moderate to severe functional disability (DAS score ≥ 2) on the principal target of treatment (1 of 4 functional domains: hygiene, dressing, malposition of the arm/wrist/fingers, and pain).
- 7. Has sufficient cognitive and communication ability to be able to give informed consent including authorization to release health information.

Exclusion Criteria

- 1. Upper limb spasticity attributable to an etiology other than stroke or TBI.
- 2. Bilateral upper limb paresis or quadriplegia.
- 3. Initiated in physiotherapy of the upper extremities ≤ 30 days prior to Screening or planned to start physiotherapy of the upper extremities during the course of the study.
- Previous treatment with any BoNT product for any condition ≤ 16 weeks prior to Screening.
- Botulinum neurotoxin treatment-experienced subjects who have historically required
 200 U of Botox/Xeomin or its equivalent to effectively treat the upper limb spasticity.
- 6. Botulinum neurotoxin treatment-experienced subjects who had suboptimal or no treatment response to the most recent BoNTA injection for spasticity, as determined by the investigator; or history of primary or secondary non-response to BoNTA injections, known to have neutralizing antibodies to BoNTA; or have a history of botulinum toxin type B (rimabotulinumtoxinB [Myobloc/Neurobloc]) injection for spasticity due to non-response or suboptimal response to BoNTA.
- Change in oral medications for spasticity including dosage and dosing frequency ≤ 30 days prior to Screening.
- 8. Previous or planned treatment of the spastic upper limb with phenol, alcohol injection or surgery.

 Profound muscular atrophy or fixed contracture (spasticity angle, per the Tardieu Scale, <10 degrees in the most hypertonic muscle group {elbow, wrist or finger flexors}) of the spastic limb leading to marked limitation on passive range of motion or any other known conditions of the upper limb that could confound muscle tone or functional assessment.

EFFICACY ASSESSMENTS

- Modified Ashworth Scale (MAS)
- Physician Global Impression of Change (PGIC)
- Disability Assessment Scale (DAS)
- Patient or Caregiver Global Impression of Change (P/CGIC)
- Tardieu Scale (TS)
- Active Range of Motion (AROM)
- Fugl-Meyer Upper Extremity (FMUE) Assessment (measure of active motor function)
- EuroQoL Five Dimension Scale (EQ-5D-5L)
- Short Form Health Survey (SF-36)

SAFETY ASSESSMENTS

- Adverse events including
- Vital signs, physical and neuro examination findings
- Injection site evaluations
- Spirometry (discontinued 20 March 2020 due to COVID-19)
- Lab tests (CBC, PT, chemistry panel, UA, urine pregnancy test [WOCBP])
- 12-lead ECG
- Concomitant medications
- Columbia-Suicide Severity Rating Scale (C-SSRS)

ENDPOINTS

Co-Primary Endpoints

 Mean change from baseline in muscle tone measured using the MAS in the suprahypertonic muscle group (SMG) of the elbow, wrist, OR finger flexors at Week 6

PLANNED ANALYSES

Analyses of Co-Primary Endpoints

- 1) Mean change from baseline in muscle tone measured by MAS in the suprahypertonic muscle group (SMG: elbow flexors, wrist flexors, or finger flexors) at Week 6
- 2) Mean score on the PGIC at Week 6

DSFS	Drooling Severity and Frequency Scale
DSMB	Data Safety Monitoring Board
ECG	Electrocardiogram
eCRF	electronic case report form
EQ-5D-5L	EuroQoL Five Dimension Scale (EQ-5D-5L)
ET	early termination
FMUE	Fugl-Meyer Upper Extremity
GCP	Good Clinical Practice
ICH	International Conference on Harmonization
IgE	Immunoglobulin E
IgG	Immunoglobulin G
IgM	Immunoglobulin M
IM	Intramuscular
INR	International Normalized Ratio

Abbreviation	Definition
IRB	Institutional Review Board
ITT	intent-to-treat
IWRS	Interactive Web Randomization System
kDa	Kilodalton
MAS	Modified Ashworth Scale
MMRM	mixed model repeated measures
NOAEL	no observed adverse effect level
PI	principal investigator
РР	per protocol
РТ	prothrombin time
PTT	principal treatment target
QoL	quality of life
QT	time from start of the ECG q wave and the end of the t wave
Revance	Revance Therapeutics, Inc.
RT002	previous name for daxibotulinumtoxinA for injection
RTP004	Revance proprietary stabilizing excipient
RTT150	previous drug substance (daxibotulinumtoxinA) name
SAE	serious adverse event
SDST	Serious Distant Spread of Toxin
SF-36	Short-Form 36
SMG	suprahypertonic muscle group
SOA	Schedule of Activities
SOP	standard operating procedure
TS	Tardieu Scale
TdP	Torsade de Pointe
TEAE	treatment-emergent adverse event
U	units (botulinum toxin)
UP	unanticipated problem
UPT	urine pregnancy test
US	United States

Abbreviation	Definition
WOCBP	women of child bearing potential

Daxibotamiantoxinit for injection for Maure opper Linib Spasier
Protocol 1820203 Amendment 2

1 INTRODUCTION

1.1 Pathophysiology of Spasticity

Spasticity is a motor symptom characterized by an increase in velocity dependent stretch reflexes, with exaggerated tendon jerks resulting from hyperexcitability of the stretch reflex, as one component of the upper motor neuron syndrome (Brashear, 2016). Spasticity is one of several abnormalities of muscle tone, and is characterized by rigidity, muscle tightness, joint stiffness, involuntary jerky movements, exaggeration of reflexes, unusual posture, abnormal positioning of fingers, wrists, arms, or shoulders, and muscle spasms. Primary causes of spasticity are anoxia secondary to cerebrovascular ischemia (stroke), trauma to the brain or spinal cord, and neurodegenerative diseases such as multiple sclerosis. (Brashear, 2011). Essentially spasticity can result from a lesion or injury anywhere along the corticospinal (pyramidal) tracks including the motor cortex, basal ganglia, thalamus, brainstem, cerebellum, central white matter or spinal cord. Fatigue, impaired coordination, impaired motor control, impaired motor planning, and muscle weakness often accompany spasticity and contribute to functional motor impairment, discomfort, and pain.

Effective treatment of spasticity is lacking. Pharmacotherapy has included baclofen (oral and intrathecal), benzodiazepines, dantrolene, phenol or alcohol injections, gabapentin, lamotrigine, cyproheptadine and cannabinoids, all with minimal success. Physical therapy, splints, casts and functional electrical stimulation have been useful to stimulate or stretch muscles and minimize soft tissue contractures. The most affected subjects may need to undergo orthopedic or neurological surgery. However, none of these methods of treating spasticity have been effective.

Recent studies have demonstrated that intramuscular injections (IM) of botulinum toxin type A shows promise in effectively relieving many spastic symptoms, particularly when combined with physical therapy (Royal College of Physicians, 2009). By preventing acetylcholine release from the presynaptic nerve terminal and thus blocking cholinergic transmission at the neuromuscular junction, botulinum toxins (BoNTs) induce a reduction in muscle contraction and muscle tone. As a result, BoNTA has become the treatment of choice for multifocal spasticity (Kaku & Simpson, 2016).

DaxibotulinumtoxinA for Injection for Adult Upper Limb Spasticity	Version 6
Protocol 1820203 Amendment 2	xx June 2020

2.1 **Primary Objective**

• To compare the safety and efficacy of a single treatment of DAXI for injection at three dose levels (250 U, 375 U, 500 U) versus placebo in reducing muscle tone of adult subjects with upper limb spasticity due to stroke or TBI

3 INVESTIGATIONAL PLAN

3.1 Overall Study Design

JUNIPER is a randomized, double-blind, placebo-controlled trial will evaluate the efficacy and safety of DAXI for injection (3 dose levels) vs placebo for the treatment of ULS after stroke or TBI in adult subjects.

Version 6 xx June 2020

Approximately 128 adult subjects with ULS after stroke or TBI will be recruited from study

3.2 Efficacy Measures

- Modified Ashworth Scale (MAS)
- Disability Assessment Scale (DAS)
- Physician Global Impression of Change (PGIC)

- Patient or Caregiver Global Impression of Change (P/CGIC)
- Spasticity per the Tardieu Scale (TS)
- Active Range of Motion (AROM)
- Active function via the Fugl-Meyer Upper Extremity (FMUE) Assessment
- EuroQoL Five Dimension Scale (EQ-5D-5L)
- Short Form Health Survey (SF-36)

3.3 Safety Measures

- Adverse events
- Vital signs, physical and neuro examination findings
- Injection site evaluations
- Spirometry (pre-COVID-19 only)
- Laboratory tests (CBC, PT/INR, chemistry panel, urinalysis)
- 12-lead ECGs
- Concomitant medications
- Columbia-Suicide Severity Rating Scale (C-SSRS)

3.4 Endpoints

- Co-Primary Endpoints
 - Mean change from baseline in muscle tone measured with the MAS in the suprahypertonic muscle group (SMG) of the elbow, wrist, OR finger flexors at Week 6
 - Mean score of the PGIC at Week 6

3.5 **Duration of Trial**

To provide a sufficient amount of time to document the duration of effect and safety profile of DAXI administered doses, all subjects will be prospectively followed for a minimum of 12 weeks and a maximum of 36 weeks. With a median duration of effect of at least 24 weeks experienced by adult subjects with cervical dystonia given a single treatment of DAXI for injection in the RT002-CL005 Study and adults with glabellar lines treated with a single treatment of DAXI for injection from the SAKURA Studies, it is scientifically justifiable to follow adult subjects with upper limb spasticity treated with DAXI for injection for up to 36 weeks.

Due to the COVID-19 pandemic impact study enrollment, visits, and conduct, subjects enrolled after the 20 March 2020 screening and enrollment hold will complete the study at Week 12. Subject participation may be terminated early for continuing or emergent safety concerns related to COVID-19. Sufficient results should be available to make informed decisions for program development.

3.6 End of Study Definition

For subjects enrolled before COVID-19, the EOS visit for a given subject can occur at Week 12 if the change in MAS score in the SMG is < 1-point reduction from baseline AND the PGIC score is ≤ 0 .

The EOS visit will occur after Week 12 when there is loss of muscle tone improvement in the SMG (i.e., a reduction from baseline in MAS score of < 1-point) AND the PGIC score is ≤ 0 .

Week 36 will be the end of study for all subjects even those who maintain the muscle tone improvement in the SMG (i.e., a reduction from baseline in MAS score of \geq 1-point) OR the PGIC score is \geq 1.

For subjects enrolled after the COVID-19 20 March 2020 screening and randomization hold the end of study will be at Week 12.

4 STUDY POPULATION

4.1 Diagnosis and Main Eligibility Criteria

Adult subjects with a diagnosis of upper limb spasticity after stroke or traumatic brain injury meeting the full eligibility criteria may participate in the study. Major inclusion and exclusion criteria are presented below.

4.1.1 Inclusion Criteria

All subjects must meet the following inclusion criteria:

- 1. Adults, 18 to 75 years of age, inclusive.
- 2. Written informed consent including authorization to release health information.
- 3. Focal ULS after a stroke (as defined by WHO criteria) or TBI, last stroke or TBI > 24 weeks prior to Screening.
- 4. Upper limb spasticity with the primary aggregate posture (AP): flexed elbow + flexed wrist + clenched fist (flexed fingers) and ≥ 1 other clinical pattern(s): adducted and internally rotated shoulder, pronated forearm, thumb-in-palm and/or intrinsic plus hand.
- 5. Moderate to severe ULS with a MAS score ≥ 2 at the elbow, wrist, and finger flexors; with the exception that the MAS score is ≥ 3 at the suprahypertonic muscle group (SMG) for subjects with previous injections of BoNTA in the paretic limb.
- 6. Moderate to severe functional disability (DAS score ≥ 2) on the principal target of treatment (1 of 4 functional domains: hygiene, dressing, malposition of the arm/wrist/fingers, and pain).
- 7. Has sufficient cognitive and communication ability to be able to give informed consent including authorization to release health information.

4.1.2 Exclusion Criteria

- 1. Upper limb spasticity attributable to an etiology other than stroke or TBI.
- 2. Bilateral upper limb paresis or quadriplegia.
- 3. Initiated in physiotherapy of the upper extremities \leq 30 days prior to Screening or planned to start physiotherapy of the upper extremities during the course of the study.
- 4. Previous treatment with any BoNT product for any condition ≤ 16 weeks prior to Screening.
- 5. Botulinum neurotoxin treatment-experienced subjects who have historically required < 200 U of Botox/Xeomin or its equivalent to effectively treat the upper limb spasticity.
- 6. Botulinum neurotoxin treatment-experienced subjects who had suboptimal or no treatment response to the most recent BoNTA injection for spasticity, as determined by the investigator; or history of primary or secondary non-response to BoNTA injections, known to have neutralizing antibodies to BoNTA; or have a history of botulinum toxin type B (rimabotulinumtoxinB [Myobloc/Neurobloc]) injection for spasticity due to non-response or suboptimal response to BoNTA.
- 7. Change in oral medications for spasticity including dosage and dosing frequency ≤ 30 days prior to Screening.
- 8. Previous or planned treatment of the spastic upper limb with phenol, alcohol injection or surgery.
- 9. Profound muscular atrophy or fixed contracture (spasticity angle, per the Tardieu Scale, <10 degrees in the most hypertonic muscle group [elbow, wrist or finger flexors]) of the spastic limb leading to marked limitation on passive range of motion or any other known conditions of the upper limb that could confound muscle tone or functional assessment.

10. Prior or current treatment with intrathecal baclofen pump.

4.4 Concomitant Medications

Concomitant medications are any prescription or over-the-counter preparations, including herbs, vitamins, or other nutritional supplements, used by subjects during participation in the study. Use of concomitant medications will be recorded on the Concomitant Medications electronic case report form (eCRF) from Screening through end of study. Subjects are allowed to be on a stable dose of medications (if any) used for spasticity treatment (e.g., anticholinergics, muscle relaxants, benzodiazepines) for at least 4 weeks prior to screening and continuing through end of study.

DaxibotulinumtoxinA for Injection for Adult Upper Limb Spasticity

4.5 Screen Failures

A screen failure subject will be an individual from whom informed consent is obtained and is documented in writing (i.e., subject signs an informed consent form) but who does not meet the study eligibility requirements.

Individuals who do not meet the criteria for participation in this study (screen failure) because of failure to meet an eligibility criterion that may requalify them after a waiting period (such as a clinically significant out of range clinical laboratory result, prohibited medication use, etc.), or because the treatment was not performed within the 21-day window after screening, may be rescreened once. Rescreened subjects may be assigned a different subject number from the one assigned at initial Screening.

4.6 Subject Discontinuation/Withdrawal Criteria

Study subjects will receive a one (1) time only treatment for this study. Discontinuation of study treatment is not applicable. However, subjects may choose to discontinue their participation in the follow-up phase at any time.

- If the subject withdraws consent and discontinues from the trial, the Investigator will attempt to determine the reason for discontinuation and record the reason in the subject's trial records and on the case report form (CRF).
- If a subject withdraws consent because of an AE, that AE should be indicated as the reason for withdrawal. In the event of early discontinuation, (i.e., prior to the Final Evaluation) and whenever possible, the subject should be asked to return to the trial center to complete the assessments specified in the Week 12/Early Termination visit. Subjects who withdraw from the trial will not be replaced.
- If at any time during the trial, the Investigator determines that it is not in the best interest of the subject to continue, the subject will be discontinued from participation.
- The Investigator can discontinue a subject from study participation at any time if medically necessary or if the subject has failed to follow trial procedures or to keep follow-up

appointments. Appropriate documentation in the subject's trial record and CRF regarding the reason for discontinuation must be completed. Prior to discontinuing a subject from study participation, the Investigator will discuss his/her intentions with the Medical Monitor or designee.

All subjects who fail to return to the trial center for the required follow-up visits will be contacted by phone to determine the reason(s) why the subject failed to return for the necessary visit or elected to discontinue from the trial. If a subject is unreachable by telephone after a minimum of two (2) documented attempts (one [1] attempt on two [2] different days), a registered letter will be sent requesting that contact be made with the Investigator.

Revance can terminate or to stop the trial at any time. Should this be necessary, both Revance and the Investigator will ensure that proper study discontinuation procedures are completed.

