10.4.2 Protocol Deviations and Compliance

A protocol deviation is any noncompliance with the clinical trial protocol. The noncompliance may be either on the part of the participant, the investigator, or the study site staff. As a result of deviations, corrective actions are to be developed by the site and implemented promptly.

It is the responsibility of the site investigator to use continuous vigilance to identify and report deviations as soon as possible. All deviations must be entered in the eCRFs and must be sent to the reviewing IRB per their policies. The site investigator is responsible for knowing and adhering to the reviewing IRB requirements.

This study will be conducted as described in this protocol, except for an emergency situation in which the protection, safety, and well-being of the subject requires immediate intervention, based on the judgment of the investigator (or a responsible, appropriately trained professional designated by the investigator). In the event of a significant deviation from the protocol due to an emergency, accident, or mistake, the investigator or designee must contact the medical monitor and the sponsor at the earliest possible time by telephone. This will allow an early joint decision regarding the subject's continuation in the study. This decision will be documented by the investigator and the medical monitor.

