3.4. Brief Description

This is a Phase 2, randomized, double-blind, placebo-controlled, parallel group, dose ranging, multi-center trial to evaluate the efficacy and safety of DAXI for injection in the treatment of ULS in adults after stroke or TBI. The trial will be conducted at approximately 30 sites across the United States.

Approximately 128 subjects with ULS will be randomly assigned

This document is confidential.

The co-primary efficacy endpoints are the mean change from baseline in muscle tone measured using the Modified Ashworth Scale (MAS) in the suprahypertonic muscle group (SMG) of the elbow, wrist, or finger flexors at Week 6 and the mean score on the Physician Global Impression of Change (PGIC) at Week 6.

- For subjects enrolled before COVID-19:
 - The end of study visit for a given subject can occur at Week 12 if the change in MAS score in the SMG is < 1-point reduction from baseline AND the PGIC score is ≤ 0 , OR
 - The end of study visit will occur after Week 12 when there is loss of muscle tone improvement in the SMG (i.e., a reduction from baseline in MAS score of < 1-point) AND the PGIC score is ≤ 0 . OR
 - Week 36 will be the end of study for all subjects, even those who maintain muscle tone improvement in the SMG (i.e., a reduction from baseline in MAS score of ≥ 1 point) OR PGIC score is ≥ 1 .
- For subjects enrolled after the COVID-19 20 March 2020 screening and randomization hold the end of study will be at Week 12.

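### Protocol 4.6 lets a treated subject be taken out of follow-up for non-compliance, which ends no exposure and can lose Week 6 and later safety data that could have been kept

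*Protocol*

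**What the plan says.** Protocol 4.6 states that subjects are treated once and that "Discontinuation of study treatment is not applicable". The same section allows the investigator to "discontinue a subject from study participation at any time if medically necessary or if the subject has failed to follow trial procedures"; the sentence goes on to add failure to keep follow-up appointments. A separate bullet in 4.6 covers removal in the subject's best interest.

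Section 4.6 also limits the rule:

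- The reason must be documented.
- Before removal, "the Investigator will discuss his/her intentions with the Medical Monitor or designee". No criteria or approval step is given.
- After early discontinuation, and whenever possible, "the subject should be asked to return to the trial center to complete the assessments specified in the Week 12/Early Termination visit".

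It adds that "Subjects who withdraw from the trial will not be replaced". No text available for review says that a subject removed for non-compliance is still asked to attend Week 6 or later visits.

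Both co-primary endpoints, MAS change in the SMG and mean PGIC, are taken at Week 6 (Protocol 3.4, SAP 4.1). SAP 5.4 requires a baseline MAS in the SMG and at least one post-baseline assessment for membership of the ITT population.

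**The concern.** A rule for ending participation usually protects a subject from further dosing. Here nothing remains to be stopped once the injection has been given, so the compliance grounds end only data collection.

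Two things are at stake. The first is the co-primary analysis. If subjects who respond poorly are also more likely to break procedures or miss visits, their removal before Week 6 leaves a selected group in the comparison. The second is safety. Protocol 3.5 justifies follow-up of up to 36 weeks by a median duration of effect of at least 24 weeks in other indications, and removal cuts that observation short. For subjects enrolled after the 20 March 2020 hold, planned follow-up already ends at Week 12, so less can be lost.

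The compliance grounds also sit badly with other parts of the protocol:

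- Section 5.1 does not automatically discontinue a subject who becomes pregnant, and gives the single administration as the reason. Section 6.4 keeps her on the trial.
- Section 4.7 tells sites to reschedule missed visits and counsel the subject.
- Section 10.7 asks for every attempt to obtain all data at the specified times.

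**Working it through.** **The plan's own figure.** SAP 3.6 gives a difference of 0.9 to 1.1 and a common SD of 1.1. Cohen's d = difference / SD, so 0.9/1.1 = 0.82 and 1.1/1.1 = 1.00. This reproduces the stated 0.8 to 1.0, and the point contests no stated number.

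**What is lost, by time of removal.**

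- Before any post-baseline MAS: both Week 6 values, ITT membership under SAP 5.4, and later scheduled safety visits.
- After a post-baseline MAS but before Week 6: both Week 6 values and later safety visits. The subject stays in the SAP's ITT population. The wording of Protocol 9.2 also mentions the 6-week MAS score and, read literally, would exclude this subject too.
- After Week 6: no co-primary value, only later efficacy and safety visits.

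**Possible bias at Week 6.** Assumptions, none taken from the documents except that the difference lies within 0.9 to 1.1:

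- true mean MAS change -1.5 on DAXI and -0.5 on placebo (difference 1.0);
- a fraction p removed before Week 6, all with zero change;
- analysis of observed values only.

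The observed mean in an arm is then (true mean)/(1 - p).

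For p = 0.10, DAXI gives -1.5/0.90 = -1.667 and placebo -0.5/0.90 = -0.556. For p = 0.05, they give -1.579 and -0.526.

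| Removal in | p = 0.05 | p = 0.10 |
|---|---|---|
| all arms | 1.579 - 0.526 = 1.05 | 1.667 - 0.556 = 1.11 |
| placebo only | 1.5 - 0.526 = 0.97 | 1.5 - 0.556 = 0.94 |
| DAXI only | 1.579 - 0.5 = 1.08 | 1.667 - 0.5 = 1.17 |

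More generally, an arm's mean shifts by p × g, where g is the gap between retained and removed subjects. For p = 0.10 in one active arm, g = 0.5 gives 0.05 points and g = 1.0 gives 0.10. Equal p and equal g in both arms cancel. They do not cancel in the all-arms row because zero change implies g = 1.67 on DAXI but 0.56 on placebo.

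**Loss of power.** The SAP says "Approximately 128 subjects with ULS will be randomly assigned". The allocation ratio is not visible, so 128/4 = 32 per arm is assumed. With SD 1.1, two-sided 0.05 and a normal approximation, power = Φ(δ / (1.1 × √(2/n)) - 1.96).

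- δ = 0.9, n = 32: Φ(3.27 - 1.96) = 90.5%.
- δ = 0.9, 10% missing (n = 28.8): Φ(3.10 - 1.96) = 87.4%.
- δ = 0.9, 20% missing (n = 25.6): 83.3%.
- δ = 1.1: 97.9% with none missing, 94.7% with 20% missing.

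These figures cover one MAS comparison, not the joint MAS and PGIC hierarchy. The power cost is modest, and possible bias matters more.

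**The case against.** The strongest reply is that the clause is permissive and fenced. It says the investigator can remove a subject, not that removal follows. It requires a documented reason and a prior discussion with the Medical Monitor. Missed visits trigger contact, rescheduling and counselling under 4.7. An early-termination visit is requested, AEs are followed to resolution (6.2.2.4), and related SAEs after last contact are reported. The trial is double-blind, and SAP 8.1.2 plans a tipping-point analysis for both co-primaries. All of this stands, and it keeps the point small.

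It does not close the gap. The early-termination visit is sought only when possible. Non-serious AEs at early discontinuation are recorded as ongoing (6.2.2.7), and new non-serious AEs after exit have no visible reporting route. The tipping-point analysis tests departures from MAR, but recovers no data and does not restore subjects outside the ITT population.

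A reader might infer more than the documents support:

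- **That removal always costs Week 6 data.** It does so only when it comes before Week 6. Follow-up runs to Week 12 or up to Week 36.
- **That removal is related to outcome.** This is plausible but not shown. Removals could be unrelated to response or balanced across arms.
- **That the primary ANCOVA uses observed values only, or that an exit assessment can never count as Week 6.** SAP 8.1.1 states no missing-data rule, and SAP Section 19 and the remapping rule under SAP 6.4 are not visible.
- **That changing an antispasticity drug or starting physiotherapy leads to removal.** Section 4.4 allows stable medication "for at least 4 weeks prior to screening and continuing through end of study" and attaches no removal consequence. The physiotherapy criterion governs entry.
- **That the person deciding on removal also scores the PGIC.** No visible text says so.
- **That section 10.4.2 is a second compliance route.** Its wording, "This will allow an early joint decision" about continuation, applies to significant deviations due to an emergency, accident or mistake, in a paragraph concerned with subject safety.

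**Conclusion.** The point holds as a cheap improvement to the protocol. It is not a flaw that undermines the trial. Section 4.6 contains a stated rule, not just an omission, that permits avoidable and possibly informative loss of Week 6 co-primary values and later safety data, with no reduction in exposure in return.

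Its size cannot be fixed from the documents. The range of 0.94 to 1.17 around a true 1.0 depends on 10% removal before Week 6, zero change in those removed, and an observed-case analysis. No document supports that removal rate. The direction is also open. If non-improvers are removed and placebo has more of them, the shift is towards 0.94, which is conservative. The 1.17 figure needs removal on DAXI alone. The tempting reading that the rule inflates the treatment effect is therefore not established.

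**What to change.** In Protocol 4.6, delete failure to follow procedures and missed appointments as grounds for ending participation. State instead that a treated subject who deviates from procedures or misses visits stays in scheduled follow-up, at least for the Week 6 and Week 12 visits, with the deviation recorded. The exceptions are withdrawal of consent, a subject who cannot be reached, and the existing medical-necessity and best-interest grounds.

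Leave those two grounds as they are, along with the emergency-deviation decision in 10.4.2. They are clinical matters and are not part of this point.

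The cost is a few words in an amendment. Sites would continue to see some poorly compliant subjects, but at visits that are already scheduled.
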